Appendix 17: Cost-effectiveness analysis

Cost Effectiveness Analysis of L-Arginine or Vitamin D supplementation to improve Pulmonary TB treatment

The study will examine the cost-effectiveness of L-arginine or vitamin D supplementation in the clinical trial setting, compared with the cost effectiveness of unsupplemented TB treatment. Comparison of the cost effectiveness between the intervention and the control groups will permit policy decisions to be made regarding funding of these potential adjuvant TB treatments, if they are shown to be beneficial.

Hypotheses :

HO : Supplementation with L-arginine or Vitamin D are not cost-effective interventions to improve pulmonary TB cure rates.

H1 : Supplementation with L-arginine or Vitamin D are cost-effective interventions to improve pulmonary TB cure rates.

Method

Data collected directly from ADAPT study participants, and additional sources described below, will be used to conduct a cost-effectiveness analysis. The Cost Effectiveness analysis is used to compare the cost and effectiveness of the intervention group (with L-arginine or vitamin D supplementation) with cost and effectiveness for standard pulmonary TB treatment (without supplementation).

Cost Measurement :

Cost information will be collected from NTP reports, government and other official documents and from study participants following previously validated methods. This information will be used to count the following costs.

- 1. Total Health System Costs: The annual expenditure for NTP (including capital and recurrent costs), to calculate the cost per patient cured. A calculation will also be made about the costs of poor compliance in terms of relapse rates for TB (and hence more cases of TB to be treated) and the potential for the development of drug resistance (and hence more expensive treatments required).
- 2. Total Patient Costs: the total cost born by the patient from diagnosis, treatment and followup during the treatment. This includes transport costs, examinations fees, loss of income and other out of pocket expenditures.
- 3. Total Opportunity Costs: The total cost forgone by community and Community Health Workers caring for TB patients.
- 4. Costs of the intervention: The costs associated with the intervention (L-arginine or vitamin D) will be calculated by including all capital, recurrent and salary costs associated with this study.

The cost will be calculated in US dollars conforming to the currency currently used in Indonesia. The costs are estimated according to the local market price. Annual value of capital items are estimated based on expected useful life of 10 years for furniture and 5 years for vehicle and equipment. The discount rate is assumed accordingly. The office buildings can be estimated to be

10% of the overhead costs.

Effectiveness :

The effectiveness will be measured through the following indicators :

- Cure rate,
- Time of sputum conversion rate
- Clinical improvement

Cost-Effectiveness Analysis (CEA)

Cost-effectiveness will calculated by dividing the total cost per activity by each different effectiveness measure using the formula:

Cost Per Patient Cure = Total Health System Costs + Total Patient Cost + Total opportunity Costs Total Number of Patient Cure

The cost per patient cure between intervention and control group will be compared and will make an inference about the cost-effectiveness of L-arginine or vitamin D intervention.

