5 STATISTICAL ANALYSES

5.1 Sample size

Sample size has been calculated using the graphical method for 2x2 factorial designs informed by the Fleiss equation, described by Byth and Gebski (71). Making a conservative assumption of sub-additive interaction between the 2 interventions (interaction coefficient of 0.5), then at a level of significance of 5%, a sample size of 444 (111 participants in each arm) will provide 82% power to demonstrate that each treatment results in a 20% reduction in the proportion culture positive at one month (from 60% to 40%), assuming loss to follow up of 10%. As there have been no trials of co-administration of vitamin D and L-arginine, the characteristics of potential immunological interactions can be extrapolated only from in vitro macrophage studies, in which findings conflict: vitamin D was found to inhibit iNOS expression in one study(44); yet upregulate NOS2A in another (68); the latter study also found the suppressive effect of vitamin D on MTB replication to be partially impaired if NO formation was inhibited. Including a sub-additive interaction term in the sample size calculation provides a margin a caution; if there is minimal or no interaction between the two interventions, our power will be greater. A factorial design rather than a three-arm study allows us to investigate whether if is safe and effective to co-administer the two interventions. Acknowledging the possibility of statistical interaction between the terms, we have an *a priori* plan to analyse primary and secondary outcomes according to subgroups receiving single interventions as well as according to the overall factorial model (71).

Mean time to culture negativity in mostly drug sensitive TB is 32 days (New York) (72) -57 days (Turkey) (73). Based on bacillary burden and extent of cavitatory disease, we estimate a minimum of 60% of Timika patients will be culture positive at 1 month. Our power will be increased if this proportion is higher. This sample size will also be powered to detect a 9% absolute difference in the mean improvement in percent predicted FEV1, a component of the composite endpoint, at 6 months. Mean baseline percent predicted FEV1 in Timika is 63.6% predicted (SD 22) rising to 77.9% predicted (SD 23) at 6 months. Each month, at least 25 eligible smear positive pulmonary TB patients are diagnosed and treated at the Timika study site. If 90% agree to be enrolled, recruitment will take <2yrs to complete.

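### The cost-per-cure formula in Appendix 17 divides the TB programme's unapportioned annual expenditure by one trial group's cures, and omits the cost of the supplements

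*Protocol*

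**What the plan says.** All of this is in the protocol's Appendix 17 unless stated otherwise.

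- Cost Measurement, item 1, defines total health-system costs as "The annual expenditure for NTP (including capital and recurrent costs), to calculate the cost per patient cured". It adds a further calculation on poor compliance, relapse and resistance. That calculation is not tied to a trial group and has no place in the formula.
- The numerator of cost per cure is "Total Health System Costs + Total Patient Cost + Total opportunity Costs". The denominator is "Total Number of Patient Cure", a count and not a rate.
- "The cost per patient cure between intervention and control group will be compared", so the ratio is formed once per group.
- The supplemented side is described as "the intervention group (with L-arginine or vitamin D supplementation"; the other side is standard treatment without supplementation.
- Item 4 reads "Costs of the intervention: The costs associated with the intervention (L-arginine or vitamin D) will be calculated by including all capital, recurrent and salary costs". It is collected but is not a term in the formula.
- Section 5.1 plans "a sample size of 444 (111 participants in each arm" and reports that each month "at least 25 eligible smear positive pulmonary TB patients are diagnosed and treated" at the Timika site.

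No cost, cure rate or cost-per-cure figure is given.

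**The concern.** The formula mixes two levels. Patient costs come from trial participants and cures are counted in one trial group, but the health-system term is a programme total for a calendar year and covers patients outside the trial. Two things follow if it is applied as written. First, the absolute cost per cure falls as the group gets larger, with no change in care or outcome. Second, the term is the same sum for every group whatever care its patients used, so groups can differ in it only through their number of cures. As item 4 is also outside the formula, the supplements' own cost does not enter the comparison. The appendix says that the comparison will inform funding decisions if the supplements prove beneficial, and such a decision needs both a meaningful absolute figure and the price of the supplement.

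**Working it through.** **Inputs from the protocol.** Arms of 111, so factorial margins of 222 and three active arms together of 333 (Section 5.1). At least 25 eligible smear-positive patients a month, so at least 25 x 12 = 300 a year (Section 5.1).

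**Assumed inputs, because the protocol gives none.** Annual programme expenditure F = 100,000 to 1,000,000; patient plus opportunity cost v = 0 to 500 per patient; cure rate c = 0.75 to 0.95, equal in the groups compared. The money values are in arbitrary units and show only direction and range.

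**Formula as written**, for a group of n patients:

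cost per cure = (F + v·n)/(c·n) = F/(c·n) + v/c

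The first term depends on n; the second does not.

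**Absolute size.** Spread over the patients it covers, the expenditure is at most F/300 per patient. Charged whole to a group it is F/n.

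- Arm of 111: 300/111 = 2.70, so at least 2.7-fold too high per patient.
- Margin of 222: 300/222 = 1.35, so at least 1.35-fold too high.

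These are minimum factors because 300 counts only eligible smear-positive patients. Example with F = 1,000,000, v = 100, c = 0.85:

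- n = 111: 1,011,100/94.35 = 10,716
- n = 222: 1,022,200/188.7 = 5,417

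The care and cure rate are the same, but the cost per cure roughly halves.

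**Comparison between equal groups** (111 v 111 or 222 v 222). With equal cure the ratio is 1.00 for every F and v in the range. If cure differs, the health-system term alone has the ratio of the cure rates inverted: for example, 0.85 v 0.90 gives 0.85/0.90 = 0.944, whatever the supplement costs.

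**Comparison between unequal groups** (all supplemented v placebo, 333 v 111), equal cure:

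- v = 0: ratio = 111/333 = 0.33
- F = 100,000, v = 500: (266,500/333)/(155,500/111) = 800.3/1,400.9 = 0.57
- F = 1,000,000, v = 100, c = 0.85: 3,651 v 10,716, ratio 0.34

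Supplementation would look 43% to 67% cheaper per cure from head-count alone.

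**After apportioning.** With F spread over M patients, cost per cure = (F/M + v)/c, and n cancels. With M = 300 and the same example values: (3,333.3 + 100)/0.85 = 4,039 in both the group of 333 and the group of 111, ratio 1.00.

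**The case against.** The appendix never says in words that the whole annual sum is charged to each group. Item 1 states its purpose as obtaining a cost per patient cured, and the appendix refers to validated costing methods, annualised capital and an overhead share. All of that fits ordinary programme costing, in which expenditure is spread over the patients served. The method of spreading could sit in an analysis plan that is not shown. This is a fair account of the likely intent. But the protocol fixes both a definition and a formula, the same label appears in each, and no unit-cost step is written. The stated rule is wrong if followed.

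A reader might infer that supplementation will look three times cheaper. The protocol does not support that as an expectation. Its wording names arginine or vitamin D but does not clearly pool all three active arms against placebo. Section 5.1 plans equal arms, a factorial analysis and single-intervention subgroups, and Section 7 uses blocks to keep numbers similar. Those comparisons carry no between-group size distortion.

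A reader might also infer that much arm-specific care is being lost. Scheduled calcium tests are the same in all arms (Section 6.1), as is the intended six-month course (Section 3.2.1). Only repeat tests, treatment of hypercalcaemia and admissions could differ.

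Finally, the glossary expands NTP as the national programme, which would make the overstatement far larger. Section 1.1.1, however, uses the term for the programme at the Timika health centre, so the local reading is the safer basis for a figure.

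**Conclusion.** The point holds as an error in a stated formula. As written, the absolute cost per cure depends on group size. Health-system cost per patient is overstated at least about 2.7-fold for an arm of 111 and 1.35-fold for a margin of 222, provided that the expenditure is that of the Timika programme and covers at least 300 patients a year. The health-system term cannot reflect differences in care between groups, and the supplements' cost is outside the ratio. Relative cost is distorted by size alone only in unequal comparisons: 0.33 to 0.57 for 333 v 111 under the assumed costs, against 1.00 for equal groups with equal cure.

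The weight is minor. The executive summary lists the economic analysis as a related study, and it is not among the primary or secondary outcomes in Section 4, which are untouched.

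**What to change.** In Appendix 17:

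1. Replace item 1 with a unit cost: the programme's annual expenditure divided by the patients, or the patient-months of treatment, that it covers. Either basis removes the dependence on group size. State which programme is meant, Timika or national.
2. Apply the unit cost to each participant and add priced recorded events that can differ by arm: admissions, hypercalcaemia management and repeat calcium tests. Sum by randomised group.
3. Add item 4, the cost of the intervention, to the numerator. Without this step, apportioning alone would still leave the supplements' cost out.

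The cost is a change of wording in one appendix and a little more analysis. The adverse-event forms already record admissions and treatment given. The number of patients the expenditure covers should be obtainable from the programme reports that the appendix already names as a cost source, though the protocol does not confirm this.

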11 FINANCING

Financing has been secured (subject to ethical approval) from the following sources indicated in Table 4. Funding bodies have indicated that funds need to be spent by the dates indicated. In particular, major in-kind contributions have been committed by the out-going MALKON director, with the expectation of use of funds commencing prior to his departure in June 2008. Pending applications are listed, and further funding applications will be made as appropriate during subsequent years of the TB project.

Equipment	Cost \$ AUD
e.g. Niox Mino® Unit, Sensorpack and NO cylinder; lung	15 600
function testing accessories.	
Study medications	
Active and placebo L-arginine and vitamin D	11 392
On-site Specimen Collection And Processing (Timika)	
Blood, sputum	13 052
Off-site Specimen Collection And Processing (Australia))
e.g. PBMC, 1,25(OH)2D3, PTH, amino acids, sputum	Costs partly absorbed by NHMRC program
	grant
Travel and local study site wages	From 2008 ARC submission
Study Participant Incentives (travel costs, snack)	\$120 000

Table 3: Funding Requirements

Table 4: Funding Sources

Funding Source	Purpose	Time frame for use	Value \$ AUD

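### Appendix 17 defines the cost of the supplements as all study costs, so item 4 does not measure the incremental cost that a funding decision needs

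*Protocol*

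**What the plan says.** Appendix 17 of the protocol examines cost-effectiveness "in the clinical trial setting, compared with the cost effectiveness of unsupplemented TB treatment", and states that the comparison between groups "will permit policy decisions to be made regarding funding of these potential adjuvant TB treatments".

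Under Cost Measurement it lists four items: health system costs, patient costs, opportunity costs and the costs of the intervention. For item 4, the costs associated with the intervention, the rule is that they "will be calculated by including all capital, recurrent and salary costs associated with this study". No sentence in the appendix limits this to supplying and delivering the supplements.

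The appendix then prints one formula, cost per patient cured. Its numerator has three terms: health system, patient and opportunity costs. Item 4 is not among them.

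Section 11, Table 3 shows what the study has to pay for. It includes an exhaled-NO unit and lung-function accessories, specimen work, participant incentives, and a medication line described as "Active and placebo L-arginine and vitamin D".

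**The concern.** A funder deciding whether to add a supplement to TB treatment needs the extra cost of supplying and delivering that supplement. Item 4 supplies a different quantity, the cost of running the study.

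The protocol itself identifies much of that cost as research. Section 3.3.5 (note 3 to the evaluation table) marks culture, exhaled NO, spirometry, the walk test, the questionnaire, the study blood tests and the weekly smears between weeks 1 and 7 as study-related. Appendix 15 describes its listed blood and urine tests as additional to standard care. Section 1.1.7 creates two research assistant posts. None of this is specific to an active arm. Participants in the double-placebo arm undergo the same evaluations, so these costs cancel in any incremental comparison.

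A single study-wide total also cannot give a separate figure for each drug. Section 3.3.3.1 gives arginine daily for eight weeks and vitamin D once every four weeks, so their delivery costs will differ.

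At stake is whether the economic analysis can answer its own question. Used as defined, item 4 could make an inexpensive supplement look poor value for reasons unrelated to the supplement.

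**Working it through.** The plan states no intervention cost, no total for Table 3 and no cost per cure, so there is no figure to reproduce. The check has two parts.

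**1. Does item 4 reach the result?** Printed numerator = health system + patient + opportunity costs. Item 1 is the annual expenditure of the national TB programme, whereas the supplements are bought from the study budget (Table 3). As printed, therefore, the charge for the supplements is zero. Item 4 affects cost per cure only if it is added.

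**2. If it is added as defined, how large could the excess be?** Table 3 serves only to illustrate this. Appendix 17 never cites it; it names programme reports, official documents and participants as sources, and local market prices for valuation. Priced lines in AUD, as the table is laid out:

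- equipment 15,600
- study medications, placebo included, 11,392
- on-site specimen collection and processing 13,052
- participant incentives 120,000

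All priced lines: 15,600 + 11,392 + 13,052 + 120,000 = 160,044. Without incentives: 160,044 − 120,000 = 40,044.

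Ratio = costs counted under item 4 / cost taken as supply and delivery.

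| Reading | Calculation | Ratio |
|---|---|---|
| All priced lines against medications | 160,044 / 11,392 | 14.0 |
| No incentives | 40,044 / 11,392 | 3.5 |
| No incentives, one fifth of equipment charged | (3,120 + 11,392 + 13,052) / 11,392 | 2.4 |
| No incentives, three fifths of equipment charged | (9,360 + 11,392 + 13,052) / 11,392 | 3.0 |
| No incentives, on-site specimen work counted as delivery | 40,044 / (11,392 + 13,052) | 1.6 |
| As the previous row, one fifth of equipment charged | 27,564 / 24,444 | 1.1 |
| As the previous row, three fifths of equipment charged | 33,804 / 24,444 | 1.4 |

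The equipment fractions use the appendix's five-year life, straight-line and undiscounted, with one to three years charged. That spread is an assumption.

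Over 444 participants, the top row is 160,044 / 444 = AUD 360 each, against 11,392 / 444 = AUD 26 for medications.

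Three things move these ratios by unknown amounts:

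- The medication line includes placebo. Removing it would raise the ratios wherever medication cost is the denominator.
- Wages, travel and off-site assays carry no figure. Their research share would raise the numerator.
- Dispensing time is also unpriced and belongs in the denominator, so unpriced wages do not all push the same way.

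**The case against.** The strongest reply is that the printed formula leaves item 4 out, so no overstatement occurs in the plan as written. If anything, the bias favours the supplements. This stands as a limit on the claim: a reader might infer that the planned cost per cure is already inflated several-fold, and the documents do not support that. It does not dispose of the point. Item 4 is listed among the costs to be counted, and the supplements cannot be assessed at zero cost, so the obvious repair of the formula would bring in the faulty value.

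A second reply is that allocation is not specified. That is correct. A reader might infer that the research budget is to be loaded onto the active arms alone, but Appendix 17 does not say so. If research costs were charged equally to all arms, every cost per cure would rise and no supplement would be singled out. The definition would still not give an incremental cost.

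Third, the sentence might mean only that capital, recurrent and salary categories are to be counted for the intervention as delivered in this trial, since the analysis is set in the trial. The wording strains against this, because it takes in all such costs associated with the study. The trial setting also does not change the stated use, which is funding policy.

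Fourth, the 14-fold figure is fragile, and this stands. Three quarters of it (120,000 / 160,044 = 75%) is incentives, which are not clearly capital, recurrent or salary costs. It charges equipment in full and divides by medications alone, although some calcium measurement might remain in routine use.

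Finally, a reader might see a contradiction with section 8.5, which describes both drugs as relatively cheap. A remark about price does not conflict with a costing rule that has not yet been applied.

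**Conclusion.** The point holds in a limited form. Item 4 as written does not exclude research-only costs, so it cannot serve as the incremental cost of either supplement. The printed formula leaves the supplements uncosted, and inserting item 4 unchanged would swap one error for another in the opposite direction.

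The size cannot be fixed from the protocol. On the priced lines of Table 3 the illustrative ratio runs from 14.0 down to 1.1, depending on whether incentives count, how equipment is annualised and how much on-site specimen work is treated as delivery. No single multiple should be quoted as the overstatement.

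The consequence is confined to the economic analysis, which the Executive Summary lists as a related study and which is not among the outcomes in sections 4.1 and 4.2. Randomisation, power, safety and the efficacy comparisons are unaffected.

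**What to change.** In Appendix 17:

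- Redefine item 4 as the incremental cost of supplying and delivering each active supplement: purchase, compounding and packaging, dispensing time, any monitoring that would be retained in routine use, and management of adverse effects attributed to it.
- State that placebo, research assays and equipment, research staff and participant incentives are excluded. Patient transport is already counted under item 2, so leaving incentives out also avoids counting travel twice.
- Cost the two drugs separately and charge each only to the arms that receive it. The combination arm carries both.
- Add this term to the numerator of the cost-per-cure formula. The two changes need to be made together.

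The cost is a few sentences in one appendix, plus a costing of drug supply and dispensing. Drug purchase is already a budget line, although its active and placebo parts must be separated. No additional data from participants are needed, and nothing in the conduct of the trial changes.

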In all instances, tests which are readily able to be performed locally will be processed in Timika. Where assays are unable to be performed in the local laboratory, samples will require storage for subsequent batched transport to MSHR and thence in some instances, to commercial laboratories for standard testing. Tests to be performed in Timika include: sputum smear microscopy, Calcium, Haemoglobin, HIV serology, and ProteomeTM Systems' rapid diagnostic (RD) test on blood, urine and sputum (when available). Tests which will be performed in Australia include sputum culture, sensitivity testing and genotyping, vitamin D and parathyroid hormone, amino acids (arginine, citrulline, ornithine), and white cell studies. Standard operating protocols are as detailed below.

Sputum Culture

There is no capacity for TB culture in Papua. We therefore propose doing sputum culture at the WHO reference laboratory, Adelaide, Australia, for the following reasons:

- 1. The laboratory in Adelaide is recognised by WHO as one of 7 global Supranational reference laboratories for TB testing. It provides this service for Australia, New Zealand, the Pacific and South-East Asia. It is within the mandate and capacity of this laboratory to provide a service to Indonesia. The WHO Supranational Reference Centre (IMVS, Adelaide) continues to collaborate with the Indonesian National TB Control Program with a range of training, guideline development and quality assurance activities.
- 2. It is our understanding that the nationally accredited TB culture laboratories in Indonesia (in Surabaya and Jakarta) are operating at maximum capacity and are fully committed to work related to the ongoing National TB drug resistance survey.
- 3. While these Indonesian laboratories therefore cannot take on the added burden of processing all sputum specimens from the ADAPT study, a regular random sample of divided specimens can be dispatched to the developing NIHRD-University of Indonesia collaborative TB Laboratory, when it becomes operational, for QA purposes.
- 4. To maintain the strong reputation of NIHRD-MSHR Research collaboration in international research and permit ongoing publication of outcomes in leading international journals, ethical and scientific integrity principles mandating participation in a quality assurance program need to be upheld. This is standard international practice in the conduct of high-quality TB research.
- 5. Our previous experience of transferring samples from Timika to the WHO reference Laboratory has been successful.
- 6. Processing of samples at the WHO reference Laboratory will provide excellent training opportunities for NIHRD laboratory scientist ([name]) to work on Indonesian samples in a supportive environment with world class training.

Vitamin D

- 1. A particular problem recognised among vitamin D assays is that of variance in results, even at the most reputable laboratories, due to unavoidable fluctuations in reagents between batches and over time. A variety of vitamin D testing methods exist, and this further increases the problem of inter-laboratory variance.(92, 93) It is recognised amongst vitamin D researchers that the variability accepted in clinical practice is too excessive according the stringent requirements of research where accurate determination within 10 nmol/L is critical. Use of standard (non-reference) laboratories for vitamin D research requires QA testing on a high proportion if not all samples, significantly elevating costs; even then, results can be difficult to interpret due to inter-test variability.
- 2. The newer liquid chromatography tandem mass spectrometry (LC-MS) method for vitamin D determination is increasingly recognised as the gold standard for vitamin D measurement. Laboratories using this method have demonstrated superior consistency of results compared with RIA or chemiluminescent assays. A laboratory offering this test has now become available in Australia (Division of Laboratory Medicine, Royal Melbourne Institute of Technology University, Victoria), and is in the process of publishing results showing superior results (lower coefficient of variance) compared with other standard vitamin D assay methodologies. This information will be forwarded to the NIHRD Ethics Committee as soon as it is available. Thus it would be in the interests of best quality research to utilise this laboratory for the measurement of vitamin D levels. The volume of blood required for LC-MS vitamin D testing is lower than that required by standard methods (100-300 microL).
- 3. Development of the LC-MS method is described by Maunsell Z et al.(94) In their discussion, they state:

"Recent publications have highlighted the interlaboratory variability of 25-OH D analysis on patient samples measured by RIA and chemiluminescence assays (24) and quality assurance material (22). In view of this, some authors have suggested that there should be international standardization of assays and have suggested that until that is achieved, RIA techniques should be used for clinical analyses (24). However, the use of a routine LC-MS/MS method offers a real alternative and negates the use of radioactive tracers."

4. The LC-MS method has been chosen as the vitamin D assay method for the UK trial of vitamin D in tuberculosis which is currently recruiting patients. The same researchers have already published results of studies of vitamin D in latent TB using the same method (see Martineau AR et al, 2007). For our study to be optimally comparable to this research, the same vitamin D assay methodology should be used.

DRAFT MATERIALS TRANSFER AGREEMENT: MSHR (Final versions in PDF format included in Regulatory Binder)

The National Institute of Health Research and Development (NIHRD), hereby referred to as the **First Party**, agrees to provide (**name, institution**), hereby referred to as the **Second Party**, with the biological specimens and / or data (Material) described in Appendix A for use in the study and for specific assays (Research Plan) described in Appendix B, under the direct oversight and responsibility of (**Scientist**). Note that both Appendix A and Appendix B are hereby considered as integral parts of this document and that the terms described herein apply to both the Institution and Scientist irrespective of their association with each other. The First Party and The Second Party agree to the following conditions:

- 1. The Material shall be used exclusively by the Second Party and be limited to the Scientist, and others as expressly stated in Appendix B, for executing the Research Plan, and for no other purpose, unless this agreement is amended in writing by expressed written consent of both parties.
- 2. The Second Party will assure that the Material is not distributed, released, or disclosed by any means, either intentional or accidental, to any person or entity other than those listed in the Research Plan. It is understood that all persons listed in the Research Plan are under the direct responsibility of the Second Party as well as the Scientist and the actions of such persons, and consequences thereof, with respect to the Material and Research Plan are thereby considered the full responsibility of the Second Party and the Scientist.
- 3. In accordance with the signed Agreement on Research Collaboration Between The Menzies School of Health Research and NIHRD (dated 12 June 2003), intellectual property rights arising from this Agreement shall be jointly owned by the First and Second Party. Both parties shall be allowed to use such property for non-commercial purposes free of royalty. Both parties are entitled to the royalties on the principle of equitable contribution if they are used for commercial purposes.
- 4. In accordance with the signed Agreement on Research Collaboration Between The Menzies School of Health Research and NIHRD (dated 12 June 2003), both parties have the same rights and access to specimens and data collected from approved studies. Upon a reasonable request made by the First Party, taking into consideration the logistics of transporting samples and whether time has elapsed since the completion of the Research Plan, the Second Party will return any and all unused Material to the first Party within thirty (30) days of written request. Costs of specimen transport will be negotiated between the First and Second Parties.
- 5. The second Party will transfer, in confidence, to the First Party any and all raw data, records, and results derived from the Material and Research Plan, including detailed records of direct use of Material. In addition, such information will be provided, where possible, within thirty (30) days of written request by the First Party.
